6.3 SUBJECT SETS ANALYSED

The Screened Set (SCR) includes all patients who signed the informed consent form and will be used to summarise patient disposition.

The Enrolled Set (ES) includes all patients who have been enrolled into the study and will be used for demographics analyses.

The Treated Set (TS) consists of all patients who have received at least one administration of any trial medication and will be used for all planned safety, efficacy and biomarker analyses in the CTRs besides the MTD determination.

The MTD Evaluation Set includes all patients from the TS who have not been replaced for the MTD evaluation; patients who has no actual replacement but satisfies the replacement criteria per protocol thus ineligible for MTD evaluation will also be excluded form the MTD Evaluation set. This set will be used for the primary analyses of DLTs and MTD determination.

Rules for replacement of patients are defined in CTP Section 3.3.4.4. The list of patients replaced for MTD evaluation or ineligible for MTD evaluation will be stored in the trial master file.

The Pharmacokinetic Parameter Set (PKS) consists of all patients in the TS who have at least one valid secondary PK endpoint available and will be used for all pharmacokinetic analyses.

[figure not shown]
The ECG Set includes all patients in the treated set who do not have an artificial pacemaker and have at least one on-treatment value for at least one ECG variable.

The ECG Pharmacokinetic Concentration Set (ECGPCS) includes all patients from the ECG Set who provide at least one time-matched pair of valid BI 891065 plasma concentration and corresponding ECG variable to be used in the exposure-response analysis.

The decision about concentration value validity needs to be made within the Clinical Pharmacology group. Refer to the [Section 7.8.4](#) for the definition of the maximum acceptable

time deviation between PK blood sampling and ECG recording at different time points during the trial.

The analysis of ECG data will be based on the ECG Set, except those analyses concerning the relationship between plasma concentrations and ECG variables which will be based on the ECGPCS. Listings for patients with artificial pacemakers will be based on the TS.

6.5 POOLING OF CENTRES

This section is not applicable since there will be no inferential analyses. Thus, no statistical model in which centre or country is included as factor will be applied.

6.6 HANDLING OF MISSING DATA AND OUTLIERS

Missing or incomplete AE dates are imputed according to BI standards (4). Missing data and outliers of PK data are also handled according to BI standards (5). Potential outliers will be reported and analysed as observed. In general, missing data not discussed in (4) and (5) will not be imputed unless required for the following analyses and definitions. Then the rules as described below apply.

1) Change of laboratory values from baseline

Laboratory values at baseline: For missing laboratory data at cycle 1 day 1 (before the first administration of any study medication) the data of preceding visits will be used if available.

2) Definition of on-treatment period and actual treatment

Date of permanent discontinuation of study medication: All reasonable efforts should be undertaken during the study to obtain the dates of permanent discontinuation of study medication. However, if the date of the very last administration is missing this will be imputed with:

- If only month and year are given, the last day of the month will be used for imputation
- If only the year is given, the 31st of December of this year will be used for imputation

If the imputed date leads to a date that is later than the date of the EOT visit, then the imputed date is the date of the EOT visit. If the imputed date leads to a date that is later than the death date, then the imputed date is the date of death.

3) Partial death dates

If a partial (year and month) death date is reported, the date will be imputed with the end of the month for the analysis of PFS. This is in line with the imputation of partial dates for the analysis of AEs.

4) Partial or missing start date of subsequent anti-cancer therapy/subsequent radiotherapy

If the day of the start date of subsequent systemic therapy/subsequent radiotherapy is missing, then the 1st of the month will be imputed unless this leads to a date before the stop date of study medication. In this case the stop date of study medication +1 day will be imputed.

If day and month, or day and month and year are missing, it will be distinguished whether the start date of subsequent systemic therapy/subsequent radiotherapy is required for censoring of PFS or for other descriptive statistics:

- For censoring of PFS: If only the year is reported, the 1st of January of this year will be imputed unless this leads to a date before the stop date of study medication. In this case the stop date of study medication +1 day will be imputed. In case of a completely missing start date of subsequent anti-cancer therapy/subsequent radiotherapy and the patient did not have any post-baseline tumour assessment or did not progress or die, the PFS of this patient will be censored at the day of first administration of BI 836826. Additionally, all imputed start dates of subsequent anti-cancer therapy/subsequent radiotherapy should be before death date, if available.
- For descriptive statistics: Dates will not be imputed if more than only the day of the date is missing.

5) ECG analysis

Quantitative and derived categorical ECG endpoints

- If single cardiac cycles are missing, the arithmetic means per single ECG will be computed with the reduced (1, 2 or 3) number of cardiac cycles.
- If replicate ECG recordings are missing, the arithmetic means per time point will be computed with the reduced (1 or 2) number of recordings.
- If the actual times of all triplicate pre-dose ECG recordings on Day 1 or the time of the first drug administration are missing, or the planned pre-dose ECGs are recorded after the first drug administration, they will not be used as baseline values and will be excluded from the analyses.
- If baseline is missing, a QTcF/QT interval > 500 msec at any time on treatment will be a notable finding.

Qualitative ECG findings

- In case a certain qualitative ECG finding is not reported at baseline but occurring on-treatment, this will be categorized as a 'new onset' of this finding.
- For the analysis of overall ECG interpretation values (comparison of on-treatment with baseline results), missing values will be handled as indicated in the following table.

Table 6.6: 1 Interpretation of qualitative ECG findings

Condition: Overall ECG interpretation		Aggregated result presented in Table
At baseline	On treatment (specific time interval under consideration)	Overall ECG interpretation
Normal, abnormal or unable to evaluate	Normal (all time points)	Normal
Abnormal	Abnormal (at least one time point)	Abnormal, and abnormal at baseline
Normal or unable to evaluate	Abnormal (at least one time point)	Abnormal (new onset)
Normal, abnormal or unable to evaluate/missing	Unable to evaluate (at least one time point), normal or unable to evaluate/missing at the other time points	Unable to evaluate/missing

Exposure-response analysis

- Missing BI 891065 plasma concentration data which are identified by BLQ (below lower limit of quantification) will be replaced by zero if measured at baseline and by ½ LLOQ (lower limit of quantification) if measured on-treatment.
- If the actual sampling time of the blood sample or of the ECG recording is not available, the pair of plasma concentration and time-matched ECG endpoint will be excluded from the analyses at the corresponding planned time point. Furthermore, plasma concentration data will be excluded from the ECG exposure-response analyses, if it is excluded from all calculations in PK analysis.

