4. TREATMENTS

4.1 INVESTIGATIONAL TREATMENTS

4.1.1 Identity of the Investigational Medicinal Products

Patients will receive either BI 891065 monotherapy or BI 891065 in combination with BI 754091 (see [Table 4.1.1: 1](#) and [Table 4.1.1: 2](#)).

Table 4.1.1: 1 BI 891065

Substance:	BI 891065
Pharmaceutical formulation:	Film-coated tablets
Source:	Boehringer Ingelheim Pharma GmbH & Co. KG
Unit strength:	5 mg, 20 mg, 50 mg, 100 mg tablets
Posology	Once daily (q.d.) or twice daily (b.i.d.), individual dose depending on dose escalation
Route of administration:	Oral

Table 4.1.1: 2 BI 754091

Substance:	BI 754091
Pharmaceutical formulation:	Solution for infusion after dilution
Source:	Boehringer Ingelheim Pharma GmbH & Co. KG
Unit strength:	20 mg/mL (vial with 15 mL filling volume)
Posology	Infusion on day 1 of 21-day cycles
Route of administration:	Intravenous infusion

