3. INTRODUCTION

As per International Conference on Harmonisation E9 (ICH E9) (1) the purpose of this document is to provide a more technical and detailed elaboration of the principal features of the analysis described in the protocol, and to include detailed procedures for executing the statistical analysis of the primary and secondary variables and other data.

This Trial Statistical Analysis Plan (TSAP) assumes familiarity with the Clinical Trial Protocol (CTP), including Protocol Amendments. In particular, the TSAP is based on the planned analysis specification as written in CTP Section 7 “Statistical Methods and Determination of Sample Size”. Therefore, TSAP readers may consult the CTP for more background information on the study, e.g., on study objectives, study design and population, treatments, and definition of measurements and variables.

The study is a multicentre study consisting of three study parts. Part A is an open-label, dose-escalation of BI 891065 alone. Part B is an open-label dose-escalation of BI 891065 in combination with a fixed dose of BI 754091. Part C consists of an expansion cohort in non-small cell lung cancer (NSCLC).

For the primary objective of the separate parts of the trial, refer to Section 2 of the CTP.

[figure not shown]

In the following, study medication always refers to BI 891065 in Part A, and to BI 891065 and/or BI 754091 in Parts B and C.

SAS[®] Version 9.4 or higher will be used for all analyses besides pharmacokinetic (PK) analyses if not specified otherwise. WinNonlin Version 8.1 will be used for PK analyses.

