Subsequent anti-cancer therapy started before progression according to RECIST v1.1 or death, no more than one consecutively missed radiological assessments prior to start of subsequent anti-cancer therapy	Censored	Date of last radiological assessment before initiation of subsequent anti-cancer therapy

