6.7 BASELINE, TIME WINDOWS AND CALCULATED VISITS

Study days and visits will be labelled according to the flowchart in the CTP.

Unless otherwise specified baseline is defined as the time point closest to but prior to the first administration of any study medication. If no time is specified and the date is the same as the first administration date, then it will still be considered baseline if not specified otherwise. If there is no measurement earlier than the first administration of study medication, then no baseline will be derived.

Laboratory values:

Baseline is defined as the latest time point before the very first administration of any study medication. For laboratories where not only the examination date but also time are recorded, examination time has to be taken into account when defining baseline. That is, a laboratory value on the same date as the first administration of study medication is considered as baseline value if and only if the time of laboratory assessment is before or the same as the time of first study drug administration.

If any of these times is missing and the date of laboratory assessment is equal to the date of first administration of study medication, then the laboratory assessment will be considered as according to protocol, i.e. as prior to first study medication.

Imaging time windows:

In order to identify whether consecutive imaging time points are missing for a given patient, a nominal time point (6, 12, ... weeks etc.) will be assigned to each and every image. This is achieved by creating windows for every radiological response assessment. These windows are defined in Table 6.7: 1.

Table 6.7: 1 Nominal time points and windows for imaging

Nominal time point (weeks from start of study medication)	Due date of scans (days)*	Window (days)
6	43	1 to ≤ 64
12	85	65 to ≤ 106
18	127	107 to ≤ 148
24	169	149 to ≤ 200
33	232	201 to ≤ 263
42	295	264 to ≤ 326
51	358	327 to ≤ 389
Etc., 9 week interval	Etc.	Etc.

* the date of the first dose of study medication is Day 1

If a patient does not have an image in one of the windows described above, he/she will be said to have missed an assessment for that time point.

ECG analysis:

Baseline values will be derived from the 1-3 triplicate ECG recordings prior to the first drug administration on Day 1 (refer to [Section 7.8.4](#)).

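### The SAP's PFS rule for a wholly unknown start date of new therapy censors at first dose of a drug not in this trial and, even with the drug corrected, discards usable follow-up and some deaths

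*SAP*

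**What the plan says.** SAP Section 6.6, item 4, sets out how to handle partial or missing start dates of subsequent anti-cancer therapy or radiotherapy when they are needed to censor PFS.

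- **Part of the date known.** If only the day is missing, the first of the month is imputed. If only the year is known, 1 January is imputed. In both cases, if the result falls before the stop of study medication, it is moved: "In this case the stop date of study medication +1 day will be imputed".
- **Nothing known.** The rule opens "In case of a completely missing start date of subsequent anti-cancer therapy/subsequent radiotherapy" and adds a second condition, that "the patient did not have any post-baseline tumour assessment or did not progress or die". Then "the PFS of this patient will be censored at the day of first administration of BI 836826".

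On the drugs of this trial, SAP Section 3 states that "study medication always refers to BI 891065 in Part A, and to BI 891065 and/or BI 754091 in Parts B and C", and Protocol Section 4.1.1 states "Patients will receive either BI 891065 monotherapy or BI 891065 in combination with BI 754091". BI 836826 appears nowhere else in the supplied documents.

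For duration of objective response, SAP Table 5.2.2: 1 sets the censoring date, when new therapy starts before progression or death, as "Date of last radiological assessment before initiation of subsequent anti-cancer therapy".

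**The concern.** There are two problems, and correcting the first does not remove the second.

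First, the censoring date does not exist. No patient in this trial receives BI 836826, so a programmer must choose a substitute date without instruction.

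Second, the obvious substitute, first administration of study medication, gives wrong results because of how the conditions are joined. A patient followed with clean scans for months, who then switched therapy on an unknown date, is treated as never observed. A patient who died before any post-baseline scan loses the event. Not knowing when a later therapy began does not invalidate scans taken on study drug, and it does not undo a death.

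Efficacy in Parts A and B is presented by dose cohort (SAP Section 7). The MTD-evaluable counts in Protocol Section 7.1.2 are 1 to 6 per dose in Part A and 5 to 8 in Part B, so one misclassified patient would be visible in a cohort's PFS summary. Those are 2019 counts. Efficacy uses the Treated Set, whose final cohort sizes are not given.

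**Working it through.** The plan gives no figure to reproduce. The check is of wording and logic, followed by a sizing.

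**1. Who is caught.** Given a completely missing start date:

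| Post-baseline scan | Progression or death | Caught as worded (*or*) | Caught if *or* were *and* |
|---|---|---|---|
| No | No | Yes | Yes |
| No | Yes (death) | Yes | No |
| Yes | No | Yes | No |
| Yes | Yes | No | No |

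The wording catches three of the four combinations. Day 1 censoring is reasonable only for the first, where nothing was observed after baseline.

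**2. Follow-up lost by a scanned, event-free patient.**

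Inputs:
- SAP Table 6.7: 1 gives scan due dates, with the note that "the date of the first dose of study medication is Day 1". Due day = 7 × week + 1, which matches all seven rows.
- SAP Section 7 converts by months = days × 12 / 365.25.
- Assumption: PFS = outcome date − first dose date + 1, because the PFS definition is not in the public text.
- BI 836826 is read as study medication. Censoring at first dose then gives 1 day, or 1 × 12 / 365.25 = 0.03 months.

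| Last clean scan | PFS to that scan | Months | Days lost by Day 1 censoring |
|---|---|---|---|
| Week 6 | 43 days | 1.41 | 42 |
| Week 12 | 85 days | 2.79 | 84 |
| Week 18 | 127 days | 4.17 | 126 |
| Week 24 | 169 days | 5.55 | 168 |
| Week 33 | 232 days | 7.62 | 231 |

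**3. Direction.** Take ten invented patients: events at days 43, 43, 43, 85, 85 and 127; censored at days 85, 169, 169 and 169. The Kaplan-Meier estimate at day 85 is (7/10) × (5/7) = 0.50.

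- *Scanned, event-free patients moved to Day 1.* With one patient from day 169 moved, it is (6/9) × (4/6) = 0.44. With two, (5/8) × (3/5) = 0.38. With three, (4/7) × (2/4) = 0.29. The estimate falls because these patients leave the risk set before any event.
- *A death without a scan moved to Day 1.* Suppose one day-43 event is such a death. Censored at Day 1, the estimate is (7/9) × (5/7) = 0.56. It rises because an event has been removed.

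These data are assumed and show direction only.

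**4. Consistency within the SAP.** The partial-date rules never place the start of new therapy before the end of study medication. The duration-of-response table keeps follow-up to the last scan before new therapy. Only the completely missing date sends the patient back to Day 1, and the SAP gives no reason for the change.

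**The case against.** The strongest reply is that this is a wrong drug code in a rule that may never be used. The SAP's own definition of study medication shows how to correct it. The trigger needs day, month and year all to be missing, whereas Protocol Section 6.2.3.3 asks sites to record the date of any subsequent therapy. PFS is neither a primary nor a secondary endpoint (SAP Sections 5.1 and 5.2.2), and no inferential analysis is planned. The PFS definition and any censoring table for it are not in the supplied text, so how PFS treats new therapy in general cannot be seen. The sentence is also loosely built, and its author may have meant only patients with neither scan nor event.

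Most of this stands as a limit on importance. It does not rescue the rule. The sentence is unredacted current text in an SAP last revised on 21 December 2020. Substituting the correct drug leaves the *or* in place. If *and* was meant, the SAP needs to say so and also state what happens to scanned, event-free patients. Such patients are plausible, because follow-up for progression ends when new anti-cancer therapy starts (Protocol Section 6.2.3.3).

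A reader might go further and infer that PFS is biased downward. The documents do not support that: the same *or* also removes deaths without a scan, which acts in the opposite direction. Nor do they support a claim that reported PFS is materially wrong, since nothing shows that any patient meets the trigger.

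**Conclusion.** The rule is wrong as written. It cannot be executed literally. With BI 836826 read as study medication, it censors at Day 1 two kinds of patient who should not be: those scanned without progression or death, and those who died without a post-baseline scan.

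The size per patient is known only for the first kind: 42 days lost with a last clean scan at week 6, rising to 168 days at week 24. This rests on PFS being counted from first dose as Day 1. The net effect on a cohort's PFS has no determinable sign.

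The priority is low. The rule bears on an endpoint outside the primary and secondary lists, and only in Parts A and B, because Part C was cancelled without enrolling patients (SAP Section 4). The number of affected patients is unknown and may be zero.

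**What to change.** Replace the sentence in SAP Section 6.6, item 4, with text to this effect:

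> If the start date of subsequent therapy is completely missing and the patient has neither documented progression nor death, the start date is imputed as stop date of study medication + 1 day, and PFS is censored at the last radiological assessment before that date. If there is no post-baseline assessment and no death, PFS is censored at the first administration of study medication. Documented progression and death are not censored by this rule and are handled under the general PFS event and censoring rules.

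The opening condition is essential. Without it, a progression scan during treatment would be the last assessment before the imputed date and would become a censoring. The existing requirement that imputed start dates precede death should stay.

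The sponsor should settle two matters alongside. The general PFS rules need to cover a scanned patient with an event and a wholly unknown start date, a case that item 4 does not address. Also, the end-of-treatment visit may fall up to 14 days after discontinuation (Protocol Section 6.2.3.1), so a scan at that visit can come after stop + 1 day and would not count under this wording. That is a small, stated loss, which the sponsor may accept or amend.

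The cost is the rewriting of one SAP sentence as above and the matching line of derivation code. No new data are needed. If the analysis has already been run, the report should state which date was used and how many patients met the condition.

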Central morphological analyses of the ECGs (cardiologic assessments) will be performed by a board-certified cardiologist or equivalent. The cardiologist will interpret one ECG per time point. In case of triplicate ECG recordings per time point, this ECG will be selected randomly. In case additional (unscheduled) ECGs due to safety reasons are recorded at the study site, all ECGs of this time point including the additional ECGs will undergo interpretation. The ECG interpretation will include an overall assessment (normal, abnormal, not assessable) as well as assessments concerning rhythm, conduction, presence of myocardial infarction, ST segment deviations, T wave morphology, and U wave morphology findings.

Abnormalities detected during centralised ECG evaluation will not necessarily qualify as AEs. In case of clinically relevant abnormalities (e.g., heart blocks or large changes in interval duration) the ECG core laboratory may contact the Investigator and vice versa.

Centrally assessed ECGs will comply with the ICH E14 guidance document and supplements (R05-2311, R13-0801, R13-4095) as well as the FDA requirements for annotated digital ECGs (R09-4830).

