- Increase of QRS complex from baseline $\geq 25\%$, when the corresponding QRS complex is > 110 ms

Qualitative variables

- The overall interpretation of an ECG, which is classified as “normal”, “abnormal”, or “unable to evaluate”,
- New onset of morphological findings, where “new onset” denotes the occurrence of an on-treatment finding, while at baseline this finding was not reported. Among these, new onset of the following findings are of special interest: atrial flutter, atrial fibrillation, any degree or type of heart block, ST-segment changes, T wave abnormalities, new U waves and myocardial infarction pattern.

The occurrence of notable or qualitative ECG findings will also be derived for the aggregated on-treatment time points of the visit days where an ECG profile has been taken as well as for the overall on-treatment period.

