7.8.2 Laboratory data

The analysis of laboratory data will be descriptive in nature and will be based on BI standards (7). The same on-treatment period as considered for the analysis of adverse events will be applied for laboratory values. Patients having at least one post-baseline laboratory value will be displayed in the descriptive analyses. Patients with missing CTCAE grade at baseline or no baseline value but with post-baseline values will be displayed in a new category “missing CTCAE grade at baseline” for those laboratory parameters where CTCAE grading is applicable. CTCAE grades for applicable laboratory parameters will be calculated according to CTCAE v5.0.

For Primary laboratory tests listed in Table [7.8.2: 1](#), the following outputs will be presented:

- Descriptive statistics, including changes from baseline
- Shift tables in terms of:
 - CTCAE grade, for laboratory tests with CTCAE grade defined;
 - Upper and lower reference limits, for laboratory tests without CTCAE grades;
 - Multiples of upper reference limit for customized shift tables of ALP, ALT, AST, bilirubin and creatinine.
- Frequency of patients with potential clinically significant abnormalities.

For secondary laboratory tests listed in Table [7.8.2: 2](#), analyses will be limited to frequency of patients with potential clinically significant abnormalities.

For other laboratory tests, only listing of observed values will be presented.

Analyse of descriptive statistics should use normalized lab values. Analyses of frequencies of patients with potential clinical significance, analyses of shift, and liver function categories tables should use converted values.

Table 7.8.2: 1 Primary laboratory tests

Label	Lab test name	Direction of interest	Potential Clinical significance rule
A1AGLP	Alpha-1 Glycoprotein	High ⁴	>ULN and >baseline No CTCAE defined
ALP	Alkaline Phosphatase	High	CTCAE Grade 2 or higher ³
ALT	Alanine Aminotransferase	High	CTCAE Grade 2 or higher ³
AST	Aspartate Aminotransferase	High	CTCAE Grade 2 or higher ³
BILI	Total Bilirubin	High	CTCAE Grade 2 or higher ³
BILIND	Indirect Bilirubin	High	CTCAE Grade 2 or higher ³ using grades defined for Total Bilirubin
BILDIR	Direct Bilirubin	High	CTCAE Grade 2 or higher ³ using grades defined for Total Bilirubin
CK	Creatine Kinase	High	A ^{1,2}
CREAT	Creatinine	High	>1.5xULN and >baseline Ambiguous CTCAE not used ³
GLUC	Glucose	Low, High ⁴	Low: A ^{1,2} High: >10 mmol/L and > baseline No CTCAE defined

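### The ECG new-onset rules in SAP 5.4.3, 6.6 and Table 6.6: 1 pool normal and unevaluable baselines, so the count mixes real change with unknown baseline

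*SAP*

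**What the plan says.** Two rules decide what counts as new on treatment.

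- **Individual morphological findings.** SAP section 5.4.3 says that new onset "denotes the occurrence of an on-treatment finding, while at baseline this finding was not reported". Section 6.6 item 5 repeats this: "In case a certain qualitative ECG finding is not reported at baseline but occurring on-treatment, this will be categorized as a" new onset. Neither asks whether the baseline tracing could be read. Section 5.4.3 applies the definition to the findings of special interest, among them heart block, atrial fibrillation, ST-segment and T wave changes and infarction pattern.
- **Overall interpretation.** In the third row of Table 6.6: 1 the baseline condition is "Normal or unable to evaluate". With at least one abnormal on-treatment time point, both kinds of patient receive the single new-onset label.

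For laboratory data, SAP section 7.8.2 takes another route: "Patients with missing CTCAE grade at baseline or no baseline value but with post-baseline values will be displayed in a new category", labelled as a missing baseline grade.

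SAP sections 6.7 and 7.8.4 derive the ECG baseline from one to three pre-dose triplicates on Day 1. Section 7.8.4 averages the interval measurements. Neither section says how the qualitative readings are combined.

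**The concern.** New onset is a statement about change. If the baseline could not be read, the on-treatment abnormality is known but the change is not. A patient who brought a stable abnormality into the trial and had an unreadable baseline is reported as having developed it on drug.

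The trial is first-in-human and has no control group, so no parallel rate exists against which to judge a new-onset count. The dose groups are small. Protocol Tables 7.1.2: 2 and 7.1.2: 5 list 1 to 8 evaluable patients per dose level at their cut-off dates. In a group of 8, one patient moves a percentage by 1/8 = 12.5 points, and in smaller groups by more. SAP section 7.8.4 plans frequency tables for these categories, so the mixed count would reach the report.

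**Working it through.** The plan states no figure for this point, so there is none to reproduce. The check is a reading of the rules followed by an illustration of size.

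**1. Table 6.6: 1, row by row**

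| Row | Baseline allowed | On treatment | Shown as |
|---|---|---|---|
| 1 | normal, abnormal, unevaluable | normal at all time points | normal |
| 2 | abnormal | at least one abnormal | abnormal, also at baseline |
| 3 | normal, unevaluable | at least one abnormal | new onset |
| 4 | normal, abnormal, unevaluable or missing | at least one unevaluable, none abnormal | unevaluable or missing |

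Row 3 joins a known change (normal to abnormal) with an unknown one (unevaluable to abnormal). Only row 4 names a missing baseline, so a missing baseline with an abnormal on-treatment ECG has no row. At finding level the same patient is new onset, because nothing was reported at baseline. The two displays can therefore treat one patient differently.

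**2. Do such patients stay in the analysis?** Yes. The ECG Set (SAP 6.3) requires an on-treatment value but no baseline. SAP 6.6 itself foresees a missing ECG baseline in its rules for the quantitative variables.

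**3. How often is a baseline unevaluable?** The documents give no rate. Protocol Table 10.3: 1 has three pre-dose triplicate time points in Part A; Tables 10.3: 2 and 10.3: 3 have two in Part B. Protocol 5.2.4 has the cardiologist interpret one ECG per time point: "In case of triplicate ECG recordings per time point, this ECG will be selected randomly". Let q be the chance that one pre-dose reading is unevaluable, assumed independent between time points.

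- If the baseline is unevaluable only when all readings are: q³ in Part A, q² in Part B.
- If one unevaluable reading is enough: 1 − (1 − q)³ and 1 − (1 − q)².

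| q (assumed) | All needed: A / B | One enough: A / B |
|---|---|---|
| 1% | 0.0001% / 0.01% | 3.0% / 2.0% |
| 5% | 0.0125% / 0.25% | 14.3% / 9.8% |

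The undefined combination rule thus decides whether the problem is negligible or not.

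**4. Share of the new-onset row that comes from unevaluable baselines.** Let b be the share of baselines that are unevaluable, p the share of patients with a pre-existing abnormality that persists, and t the true new-onset rate among those normal at baseline. All three are assumptions.

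- True changes with a readable normal baseline: (1 − b)(1 − p)t
- From unevaluable baselines: b[p + (1 − p)t]
- Share = second / (first + second)

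With p = 40% and t = 20%:

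| b | First | Second | Share | Of the whole row, actually pre-existing, bp / (first + second) |
|---|---|---|---|---|
| 1% | 0.1188 | 0.0052 | 4.2% | 3.2% |
| 5% | 0.1140 | 0.0260 | 18.6% | 14.3% |
| 10% | 0.1080 | 0.0520 | 32.5% | 25.0% |

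Over p = 20–60%, t = 10–20% and b = 1–10%, the share runs from 2.2% (p = 20%, t = 20%, b = 1%: 0.0036/0.1620) to 64% (p = 60%, t = 10%, b = 10%: 0.064/0.100). Among the combinations tried, it exceeds one half only at that last one.

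**The case against.** The best defence is that the rule is a deliberate safety convention: when in doubt, count it. The same list in SAP 6.6 counts a QTcF or QT above 500 ms as notable when the baseline is missing. The analysis is descriptive, individual ECG data are listed, and clinically relevant findings are also analysed as adverse events. Protocol exclusion criterion 10 keeps out clinically important rhythm, conduction and morphology abnormalities. Protocol 5.2.4 allows recordings to be repeated for quality, so an unevaluable baseline may be uncommon.

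Much of this stands. The error is on the cautious side, a reader can trace a patient through the listings, and the frequency may be low. The 500 ms rule is not a true parallel, though. It is an absolute threshold that means something without a baseline, whereas the label new onset has no meaning without one. Criterion 10 leaves lesser abnormalities in. Listings help a reader who goes looking, but they do not correct the table. A separate row is just as cautious, because it hides nobody.

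A reader might go further and infer that the new-onset category reflects missing data rather than change on drug. The documents do not support that. Row 3 requires an actual abnormal on-treatment reading, and it contains every real change from normal to abnormal.

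A reader might also object to row 4, where one unevaluable time point takes an otherwise normal patient out of the normal category: "Unable to evaluate (at least one time point), normal or unable to evaluate/missing at the other time points". That row is openly labelled as unevaluable or missing, and it never hides an abnormal reading, since any abnormal time point leads to row 2 or 3. Any percentage for its effect would rest on an assumed unreadable rate, would have to allow for repeat recordings, and would be smaller in the tables that SAP 7.8.4 also plans by visit day. Deriving normal from the evaluable time points alone has its own cost. Part A has 9 + 1 + 10 + 1 = 21 on-treatment triplicate time points on Days 1, 2, 15 and 16, and a patient with one readable normal tracing among them would be called normal.

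**Conclusion.** The point holds for the new-onset rules only. SAP 5.4.3, 6.6 item 5 and row 3 of Table 6.6: 1 put known and unknown change under one label, while the laboratory section of the same SAP separates them. That follows from the text and needs no assumption.

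The size is not known. The share of the row that comes from unevaluable baselines depends on a rate that the documents do not give and on a baseline definition that they leave open. It may be close to zero; under the assumptions shown it ranges from 2.2% to 64%. No hypothesis test is affected. What is affected is how a small, uncontrolled safety count reads. The row 4 rule is acceptable as written. SAP section 4 states that Part C was cancelled without enrolling patients, so Parts A and B alone are concerned.

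**What to change.** Change the SAP as follows:

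1. Split row 3 of Table 6.6: 1 in two: *abnormal (new onset), baseline normal* and *abnormal, baseline not evaluable or missing*.
2. Let the second of these rows cover a missing baseline explicitly, since rows 1 to 3 do not name it.
3. Apply the same split to individual morphological findings in sections 5.4.3 and 6.6 item 5. A finding is then new onset only if an evaluable baseline did not show it.
4. State how the qualitative readings from the one to three pre-dose time points combine into one baseline, and when that baseline counts as unevaluable.
5. Leave row 4 as it is. If wanted, show the number of unevaluable time points beside it.

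The cost is a few lines of SAP text and one derivation change, with no new data. The small downside is that the new-onset count is no longer a worst-case count, but the patients moved out of it stay visible in their own row.
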